	Academic Respiratory Unit		
	University of Bristol [name]		
	North Bristol NHS Trust		
	Southmead Hospital		
	Bristol		
	[name]		
	E-mail: [contact]		
Trial Co-ordinator	[name]		
	Pleural Clinical Research Fellow		
	Academic Respiratory Unit		
	University of Bristol		
	[name]		
	North Bristol NHS Trust		
	Southmead Hospital		
	Bristol		
	[name]		
	E-mail: [contact]		
	[contact]		
Sponsor	North Bristol NHS Trust		
Sponsor	Southmead Hospital		
	Bristol		
	[name]		
	[contact]		
Funders			
	Rocket Medical plc		
	[name]		
	WATFORD		
	[name]		
	[contact]		
Trial Management Committee and Key Protocol	[name]		
Contributors	[name]		
	[name]		
	[name] [name]		

Contents

Chief investigator & Research Team Contact Details	1
Signature page	3
Key trial contacts:	4
List of abbreviations	6
Trial summary	7
Funding and support:	7
Study Flow Chart	8
Plain English Summary	8
Background	9
Aims & Objectives:	11
Aims and objectives:	11
Clinical outcomes	11
Methodology	11
Study design	11
Study population	12
Recruitment	12
Figure 1: Opt-out consent Flow chart	13
recruitment target	13
Follow-up schedule	14
Figure 2: Patient journey flowchart	15
Data collection	15
Study flow chart:	16
Definition of end of trial	17
Data handling and record keeping	17
Statistical considerations	18
Finance and Insurance	20
Reporting and Dissemination	20
References	21

LIST OF ABBREVIATIONS

COPD	Chronic obstructive pulmonary disease	
СТ	Computed tomography	
CXR	Chest X-Ray	
DAL	Digital air leak	
EQ-5D-5L	EuroQol 5D Health Questionnaire	
ICD	Intercostal chest drain	
NBT	North Bristol NHS Trust	
PAL	Persistent air-leak	
PIS	Participant information sheet	
PPI	Patient and public involvement	
PSP	Primary spontaneous pneumothorax	
PS	Performance status	
SP	Spontaneous pneumothorax	
SSP	Secondary spontaneous pneumothorax	
VAS	Visual Analogue Scale	

TRIAL SUMMARY

Trial title	LONGITUDINAL INVESTIGATION OF SECONDARY PNEUMOTHORAX		
Short title	LISP		
Trial design	Longitudinal observational study		
Trial participants	Population of interest: patients presenting to hospital with secondary		
	spontaneous pneumothorax		
Planned recruitment	60 patients/year minimum		
rate			
Planned trial period	1 years		
Trial objectives	To determine the characteristics, healthcare burden, management,		
	and outcomes of secondary spontaneous pneumothorax (SSP) in UK		
	over a 1-year period		
Inclusion criteria	Emergency attendance to hospital with secondary spontaneous		
	pneumothorax, confirmed by radiology, with SSP defined as:		
	 spontaneous pneumothorax in presence of known or 		
	suspected lung disease OR		
	 spontaneous pneumothorax in patient ≥50 years of age and 		
	smoking history		
Exclusion criteria	Exclusion		
	 age <16 years of age 		
	iatrogenic pneumothorax		
	traumatic pneumothorax		

FUNDING AND SUPPORT:

Funders	Financial and non-financial support given
Rocket Medical plc	Unrestricted research grant and equipment
[name]	
Watford	
[name]	
[contact]	

Role of trial Sponsor and Funder:

The Sponsor and Funders have no role or remit in the trial design, conduct, data analysis and interpretation, manuscript writing or dissemination of results.

Protocol contributors:

Protocol authors: [name], [name], [name], [name], [name].

External Peer review

National INSPIRE committee: [name], [name], [name], [name], [name]

STUDY FLOW CHART

PLAIN ENGLISH SUMMARY

Background

Secondary spontaneous pneumothorax (SSP) is a medical emergency where an abnormal collection of air develops in the space between the lung and the chest wall, causing lung collapse. This occurs in patients with existing lung disease such as Chronic obstructive pulmonary disease (COPD). In the UK, patients with SSP are usually treated by inserting a drain into the chest to remove the air. The drain is stitched in place and left until the air is completely removed. The drain typically remains in place for over a week, leading to long hospital stays. Sometimes these patients need surgery to help stop the air leaking into the lung, but it is also recognised that these patients may not be fit for major surgery.

Unfortunately, we don't have data from UK patients about key consequences of developing a secondary spontaneous pneumothorax. For example, we don't know how long patients stay in hospital, how many go for surgery, and how many develop complications. With this information we can better plan for care, but also look at why some patients stay longer in hospital and why some patients need surgery, whilst others don't.

The aim of this study is to gather information about SSP in an attempt to answer some of these unknown questions. We will recruit patients admitted to hospital with SSP throughout the UK over a period of 1 year. We will collect routine data from the patients' records, such as age, medical history and how long they stay in hospital.

Patient and public involvement

We had discussions with patients and conducted a survey to find out what outcomes were most important to them. Patients told us that length of hospital stay was really important and also that they want treatments that aren't painful. We used this feedback to design this study.

Dissemination

The findings of these study will help us decide on the best care for patients and help us plan for future research projects. We will work with social media groups to let patients and doctors know the findings, write up our results in journals and present at conferences. We will work with key professional societies to incorporate our findings into relevant guidelines.

BACKGROUND

Spontaneous pneumothorax is a common acute medical emergency, where an abnormal collection of air forms in the space between the lung and the chest wall, causing collapse of the lung. It can be subclassified as primary spontaneous pneumothorax (PSP) or secondary spontaneous pneumothorax (SSP) depending on absence or presence of lung disease. PSP occurs in patients typically in young adults, between the ages of 15 and 35 who do not have lung disease. SSP typically occurs in older patients and is secondary to patients' existing chronic lung disease. It can be an acute medical emergency when the lung collapses in the presence of underlying chronic lung disease. Because of their underling lung disease, patients with SSP are typically much more breathlessness and unwell than patients with PSP.

SSP is the commonest cause of spontaneous pneumothorax, with over 3,000 patients per year admitted to hospital with SSP in England and accounts for 60% of all spontaneous pneumothorax (SP). However, the literature base for SSPs is much smaller than that for PSP(1). There is currently a large disconnect between trial and real-world populations; with less than 10% of the randomised studies in SP investigating SSP.

UK specific data on SSP is entirely absent, with even basic data on typical length of stay, underlying aetiology and surgical referral rates having to be extrapolated from international studies out of necessity. Currently, a single centre study from Japan and a French epidemiological study provide the best estimates for length of stay in SSP(2, 3). National databases, such as the Hospital Episode Statistics (HES) database, do not distinguish between PSP and SSP, and do not provide detailed individual patient level data.

British Thoracic Society (BTS) guidelines provide clear advice on different treatment strategies for primary (PSP) and secondary (SSP) spontaneous pneumothorax, but compliance with these guidelines amongst non-respiratory healthcare professionals is reportedly low(8). Additionally, the advice on SSP is based on limited data and there are many outstanding research questions that need answering. There is no current guidance on patient selection for surgical management for persistent air leak (PAL) and recurrence prevention. Patients with SSP are typically felt to be poor surgical candidates, due to poor physiological reserves and comorbidities, but there is a lack of information about which patients would most benefit and which are most are risk. This project would identify the patient characteristics of those accepted for surgery, and their outcomes. Additionally, the management of persistent air leak is extremely problematic in this patient cohort, with no clear evidence on how best to manage. This project would capture current national practice on PAL and the impact this had on air leak duration.

Recurrence rates are felt to be higher in SSP compared to PSP, with historic and poorly evidenced cited rates between 40-50%(5), however there is no robust data to inform on this, or the factors which influence it. This project would give vital insights and help inform practice.

10

AIMS & OBJECTIVES:

To determine the characteristics, healthcare burden, management, and outcomes of secondary spontaneous pneumothorax (SSP) in UK over a 1-year period

AIMS AND OBJECTIVES:

- To determine characteristics of SSP patients admitted in study period (age, gender, underlying respiratory condition)
- To determine management of SSP in study period (procedures, recurrence prevention, surgery)
- To determine outcomes of SSP admission (length of stay, duration of air leak, mortality)
- To determine factors, including inter-site variability, influencing surgical referral and acceptance rates for air leak and recurrence management
- To determine factors influencing short-term recurrence rates

Research questions which may be addressed as part of the study are listed below.

CLINICAL OUTCOMES

- 1. What are the demographics of the SSP population in the UK (age, gender, underlying aetiology, previous SSP, lung function)?
- 2. What are the size and location of pneumothorax on chest x-ray (side, maximum intrapleural distance, hilar intrapleural distance)?
- 3. How are the patients managed during their inpatient stay (initial management, prolonged air leak management, recurrence prevention interventions, surgical referral, surgical intervention)?
- 4. What are the patients' length of stay?
- 5. What are the patients' duration of air leak?
- 6. What are the patients' mortality rate?
- 7. What proportion are referred and receive surgery?
- 8. What are the patients 6-month ipsilateral recurrence rates?
- 9. What is the expertise available at hospital (presence of onsite thoracic surgical unit, dedicated pleural clinic)?

METHODOLOGY

STUDY DESIGN

LISP is a multi-centre, prospective, longitudinal cohort study of patients diagnosed with SSP.

STUDY POPULATION

Population of interest: patients presenting to hospital with secondary spontaneous pneumothorax.

Inclusion

Emergency attendance to hospital with secondary spontaneous pneumothorax, confirmed by radiology, with SSP defined as:

- spontaneous pneumothorax in presence of known or suspected lung disease OR
- spontaneous pneumothorax in patient \geq 50 years of age and smoking history.

Exclusion

- age <16 years of age
- iatrogenic pneumothorax
- traumatic pneumothorax

RECRUITMENT

Recruitment procedure

Research in an emergency setting is always challenging due to high clinical work load and the proportion of eligible patients presenting out of hours. Clinicians have additional levels of clinical demand during night shifts and research teams are often not available to support recruitment. Additionally, patients with SSP will potentially be in significant pain/respiratory distress at the time of presentation and may have diminished capacity. However, it is vital that patients presenting out of hours with SSP are offered the opportunity to participate in this research, and it is also vital to the integrity of the research methodology that these patients are included within a consecutive sample, to ensure the findings are generalizable.

To minimize the risk of recruitment bias in our sample, this study plans to recruit 24 hours a day, 7 days a week, at all sites. To achieve this, there will be extensive departmental awareness of the study raised at each site, and we will use trained clinicians to recruit to the study as part of routine care, in addition to research teams. As such, it is essential that we minimize the administrative burden for these busy clinicians. We have chosen an opt-out consent process to facilitate this, designed to ensure patients are robustly informed and provided with tiered opportunity to ask questions/engage with the research at their preference. This method will minimize the risk of

missing a significant cohort of patients presenting between 2200 and 0800, minimize the burden on clinical staff recruiting during standard working hours, but maximise the generalisability of the research.

This study involves no change in clinical treatment and no additional interventions for participants. It therefore carries no clinical risk. It is also well recognised that patients attending the ED with SSP are in pain and at a time of acute anxiety/distress; often, they require immediate management. As such it will be impractical and potentially distressing to seek fully informed consent in an emergency setting. We will therefore adopt a proportionate approach using an opt-out strategy, as supported by the Health Research Authority (HRA).

Participation in LISP will not impact on any part of the patients' routine care and they will be entitled to withdraw from the study at any point, without giving a reason.

FIGURE 1: OPT-OUT CONSENT FLOW CHART

RECRUITMENT TARGET

A conservative estimate of patients with SSP presenting and identified by research staff at each site is 12 per annum (based on Hi-Spec RCT screening log(6)). Provisional anonymised HES data suggest that this may be a

considerable underestimate, demonstrating a mean of 40.5 SSP presentations/annum at the top 15 NHS Trusts. As SSP typically have substantial inpatient length of stay and are managed by Respiratory team, high identification rates are anticipated. Additionally, the opt-out consent model should maximize data capture. With 20 participating sites, we would expect a minimal of 120 patients over a 6-month period.

The recruitment target is a minimum of 120 patients per year. The LISP will run over a one-year period (recruiting for 6 months with a 6 month follow up period). Given the observational nature of this study, patients will be eligible to co-enrol in other studies if invited.

FOLLOW-UP SCHEDULE

All participants will only undergo assessment at a single time point, at enrolment ("baseline assessment"). This will be performed by a member of the study team and should be done within the first week from enrolment.

Subsequently, study data will be acquired from the medical records at two further time points, at 1-month and 6-months post enrolment. This will be conducted by the local medical research investigator. As this is a trainee-lead project, it is anticipated this will a respiratory trainee.

LONGITUDINAL INVESTIGATION OF SECONDARY PNEUMOTHORAX (LISP) PATIENT JOURNEY FLOWCHART **INSPIRE NETWORK**

Emergency attendance to hospital with secondary spontaneous pneumothorax, confirmed by radiology, with

- · spontaneous pneumothorax in presence of known or suspected lung disease
- spontaneous pneumothorax in patient ≥50 years of age and smoking history.
- iatrogenic pneumothorax
- traumatic pneumothorax

FIGURE 2: PATIENT JOURNEY FLOWCHART

DATA COLLECTION

Baseline assessment

The baseline assessment for all patients will incorporate routinely collected clinical information, such as:

- History and examination by a Respiratory physician, including duration of symptoms, co-morbidities and • past medical history, current/recent medications, smoking status including cannabis, clinical frailty score (CFS) and performance status (PS).
- CXR data- size of pneumothorax

1-month post-enrolment (+/- 14 days)

A review of participant's clinical records to collect data on key clinical outcomes, including but not exclusively, the:

- Initial length of stay
- Digital air leak (DAL) measurement (if available)
- Analogue air leak assessment
- Number of type of interventions, including therapeutic aspirations, intercostal chest drains (ICD) insertions, blood batch, ambulatory care and surgical procedures.
- Treatment complication
- Mortality

6 month post-enrolment (+/- 14 days)

A review of participant's clinical records to collect data to identify:

- Initial Length of stay (if exceeded 1 month)
- Ipsilateral recurrence of pneumothorax

STUDY FLOW CHART:

Schedule of assessments:

Description	Investigation	Baseline	4 -week	26-week
		assessment	follow up	follow up
			assessment	assessment
			(+/- 7 days)	(+/- 4
				weeks)

Clinical review	Patient demographics	Х		
	Pneumothorax history	Х		
	Patient co-morbidities	Х		
	Assessment of PS/CFS	Х		
	Medication history	Х		
	Number of interventions		Х	
	Mortality		Х	
	Length of stay		Х	Х
Recurrence			Х	Х
Imaging	CXR	Х		
	СТ		X*	
Air leak	Analogue air leak assessment (if		Х	
assessment	available)			
	Digital air leak assessment (if		Х*	
	available)			
*-if clinically available				

DEFINITION OF END OF TRIAL

All participants will be actively followed up for 6 months after recruitment. The opt-out log will be reviewed 4 weeks after data-collection has finished. The end of the trial as a whole will be after all trial participants have completed follow up, all data queries have been resolved, the database locked and the analysis completed.

DATA HANDLING AND RECORD KEEPING

Data collection tools and source document identification

Source data will all be electronic from NHS Trust computer systems i.e., patients' medical records, laboratory and radiology reports and directly entered onto an eCRF in REDCap.

Data handling and record keeping

Data entry at will use a bespoke study database housed on the University of Bristol server, built using the validated open-source REDCap system and regularly backed up. The study investigator will facilitate data entry into the database via an electronic case report form (eCRF) with the support of the clinical team. Each participant will be allocated an unambiguous subject identification code (trial participant ID).

REDCap includes data validation checks which are inbuilt into the database build and a data query management system to allow management of data quality throughout the trial. The LISP database will be validated as part of the Database Activation process and final data quality checks will be incorporated as part of the Database Lock process.

It is also possible to download the data for all records in this project in a single PDF file that could be printed and retained with the TMF. This file contains the actual page format as you would see it on the data entry page or survey and includes all data for all records for all data collection instruments.

Access to Data, Data Protection and Confidentiality

All data will be stored in line with Good Clinical Practice (GCP) requirements and the General Data Protection Regulation (GDPR).

All study documentation will be kept secure in an access restricted environment and only accessible by LISP study staff and authorised representatives from the Sponsor and regulatory authorities to permit trial-related monitoring, audits and inspection.

Patient data will be kept confidential. On all trial specific documents the patient will be referred to only by the trial participant ID. Only usual care team will have access to identifiable data.

REDCap is password protected with only approved users having access. User access can be restricted to different levels by assigning users with limited permissions based on their role (i.e., data entry only). Interaction with the software automatically creates an access log data trail, ensuring that the access of data can be audited to ensure data protection (e.g. by data point, function or individual user).

Archiving

Once all required downloads have been confirmed with the University of Bristol REDCap team, they will delete the study data from the REDCap project but keep the metadata and put this into archived status. This way, the project can still be brought back to life if needed (by uploading the data from long term storage) but it no longer exists on the REDCap server. Data will be retained as per NBT archiving policy.

STATISTICAL CONSIDERATIONS
Sample size calculation

The prospective descriptive nature of this observational study renders a sample size calculation unnecessary. Our aim is to recruit a minimum of 120 patients over the 6 month study period of the study would allow us to adequately assess the above research questions.

Analyses

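### The data collection plan does not secure the surgical referral and acceptance objective: interventions and air leak are scheduled only at the 1-month review, and neither referral nor acceptance is a named data item

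*Protocol*

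**What the plan says.** **Objectives.** The fourth item in the Protocol's Aims and objectives reads "To determine factors, including inter-site variability, influencing surgical referral and acceptance rates for air leak and recurrence management". The Background makes a matching promise: "This project would identify the patient characteristics of those accepted for surgery, and their outcomes". Under Clinical outcomes, question 3 on inpatient management includes "surgical referral, surgical intervention", and question 7 asks "What proportion are referred and receive surgery" with no time limit. These numbered questions are introduced permissively: "Research questions which may be addressed as part of the study are listed below". The objective stands above that sentence and is not softened by it.

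**Data collection, 1-month review.** The list is introduced as a review of records "to collect data on key clinical outcomes, including but not exclusively, the" items that follow. They include air-leak measurements and "Number of type of interventions, including therapeutic aspirations, intercostal chest drains (ICD) insertions, blood batch, ambulatory care and surgical procedures".

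**Data collection, 6-month review.** Two items are listed: "Initial Length of stay (if exceeded 1 month") and ipsilateral recurrence. There is no open-ended lead-in here.

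**Schedule of assessments.** The row for number of interventions has one mark, in the 4-week column. Both air-leak rows are likewise marked at 4 weeks only. Length of stay and recurrence are marked at 4 and 26 weeks. There is no row for referral or for acceptance.

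**Analyses.** Surgical management is named as an outcome for regression.

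**The concern.** The objective needs three things for each patient: whether a referral was made, whether it was accepted, and whether and when surgery took place. It needs them for two indications, air leak and recurrence. Recurrence is followed to 6 months, and the protocol itself foresees index admissions longer than a month, yet the listed recording of interventions ends at the first review.

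What is lost is not a random subset. Patients still in hospital at the first review have the longest stays, and prolonged air leak is a likely reason. Patients who recur in month 2 or later are those for whom recurrence surgery becomes a question. If operations and leak resolution in these groups go unrecorded, the reported surgery proportion is too low and leak durations are cut off at the review date where they are longest. If sites do not record referral in a uniform way, the comparison of referral and acceptance between sites, a stated aim, has no consistent basis.

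**Working it through.** No formula in the protocol bears on this, and there is no planned figure to reproduce. The check traces each element of the surgical objective to the places where data items are specified.

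| Element needed | 1-month list | 6-month list | Schedule table |
|---|---|---|---|
| Referral to surgery | not named (list open) | not named | no row |
| Acceptance decision | not named (list open) | not named | no row |
| Surgery up to the first review | named | – | 4 weeks |
| Surgery after the first review | – | not named | not marked at 26 weeks |
| Air leak up to the first review | named | – | 4 weeks |
| Air leak ending after the first review | – | not named | not marked at 26 weeks |
| Length of stay beyond 1 month | – | named | 26 weeks |
| Ipsilateral recurrence | – | named | 4 and 26 weeks |

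**Step 1: the time gap.** Text and table agree that interventions and air leak belong to the first review only. They also agree that length of stay is picked up again at the second. So for a patient still in hospital at one month, the plan retrieves the discharge date but lists no field for the operation or the leak closure that may have preceded discharge. For a patient who recurs in month 3, the plan retrieves the recurrence but not its treatment.

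**Step 2: referral and acceptance.** The surgery proportion can be written as

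operated / all = (referred / all) × (accepted / referred) × (operated / accepted).

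The named fields give only the left-hand side, and only up to the first review. Among patients without surgery they do not separate those never referred from those referred and declined. Acceptance among those referred therefore cannot be calculated from the named fields alone. It could be if the eCRF carries more than is named.

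**Step 3: the cut-off itself.** The first review is the end of intervention recording, so its timing matters. Taking one month as about 30 days, 4 weeks as 28 days, and 6 months as 26 weeks (182 days):

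- First review, text (± 14 days): 30 − 14 = day 16 to 30 + 14 = day 44.
- First review, table (± 7 days): 28 − 7 = day 21 to 28 + 7 = day 35.
- Second review, text (± 14 days): 182 − 14 = day 168 to 182 + 14 = day 196.
- Second review, table (± 4 weeks, 28 days): 182 − 28 = day 154 to 182 + 28 = day 210.

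The two statements disagree at both reviews. Under the text, two patients could have their interventions recorded over periods differing by up to 28 days (44 − 16); under the table, by up to 14 days (35 − 21).

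**Step 4: size.** If a fraction *f* of operations falls after the first review, a true surgery proportion *p* is reported as *p*(1 − *f*). The protocol gives neither *p* nor *f*, so the direction is known but the amount is not.

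**The case against.** The strongest reply has four parts.

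**The 1-month list is explicitly non-exhaustive, and the eCRF is not shown.** Surgical referral is also named in question 3. A reader might infer that referral and acceptance will not be collected at all, or that the acceptance rate cannot be computed. The documents do not support that: they show only that neither item is named. This part stands. It does not reach the 6-month list, which has no such wording, and an open list does not ensure that 20 sites record the same thing.

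**Surgery soon after admission is covered.** A reader might infer that none of the surgical questions can be answered. That is too broad. Surgical procedures up to the first review are listed, so the received-surgery half of question 7 and the surgical part of question 3 can be reported for that period. Question 3 is confined to the inpatient stay, and the Plain English Summary describes drains as typically in place for over a week, so a one-month review may well cover most admissions. This stands; the exposed group is those whose stay, surgery or recurrence falls later.

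**The recurrence analysis.** A reader might infer that late-operated patients will be misclassified as unoperated in the recurrence model. The protocol does not state such an analysis. The parameters named are underlying lung disease, FEV1 and recurrent pneumothorax, and surgery appears as an outcome. The parameter list is open, so surgery might be added, but even then only late surgery before any recurrence would matter. Surgery performed for a recurrence is not an exposure for that recurrence.

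**The size.** A reader might take day 16 as the cut-off and say that five of six months of surgery go unseen. Day 16 is the earliest edge of one of two conflicting windows, and calendar time is not surgical activity, which could cluster around the index admission. Assuming *p* = 20% and *f* = 10% to 30% would give 20% × 0.9 = 18% down to 20% × 0.7 = 14%, but nothing in the protocol supports those inputs.

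The permissive wording before the numbered questions does not help, since the objective itself is firm. Nor can the matter be left to an analysis plan, which cannot recover data that were not collected.

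**Conclusion.** The concern holds in a limited form. Followed as written, the protocol would miss surgery and air-leak resolution after the 1-month review, and it names no data item for referral or acceptance, although both are part of a stated objective. The surgery proportion would be biased downwards and leak duration cut short, chiefly in admissions outlasting a month. Surgery for later recurrence, or for elective recurrence prevention, would be absent. The size cannot be given, because the protocol states neither how many patients fall in these groups nor how often they have surgery.

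The time gap rests on text and table agreeing, and is the firmer part. The referral and acceptance part rests on the named items only and would be answered if the eCRF already holds those fields. The change should be made because the gap falls on the patients the objective is about and is cheap to close.

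**What to change.** 1. In the 6-month list and the 26-week column of the schedule, add interventions (type and date) and the air-leak end date.
2. At both reviews, name as data items: referral to thoracic surgery (yes/no, date, and whether for air leak or recurrence prevention) and acceptance (yes/no). If the eCRF already holds these, bring the protocol lists into line with it.
3. State that acceptance is analysed among those referred.
4. If later collection is not wanted, restrict the surgical objective and question 7 explicitly to the period up to the 1-month review.
5. Reconcile the review windows between the Data collection text and the Schedule of assessments, so that the cut-off for recording interventions is defined.

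The cost is slight: a few extra fields for the local investigators at two record reviews already planned, with no added patient contact. Option 4 costs no data entry but narrows what the study can say about surgery for recurrence and in prolonged admissions.
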